4.4.1.3 Supportive Analyses

A PP analysis will be performed on the number of bleeding sites if there is more than a 10% difference in the number of subjects between the PP and mITT populations. A decision on whether a PP analysis will be performed will be made prior to study unblinding (release of randomization codes).

A summary of the mean number of bleeding sites at each time point will be presented for the PP population in Table 14.2.2.1.2. A summary of the number and percentage of subjects at each time point whose number of bleeding sites has improved/remained the same/worsened compared to baseline will be presented for the PP population in Table 14.2.2.1.4. Statistical analysis of the mean number of bleeding sites will be presented for the PP population in Table 14.2.2.2.2. In addition, the mean number of bleeding sites at each time point will be plotted by study product for all subjects in the PP population (Figure 14.2.2.1.6).

In order to explore the sensitivity of results to the effect of missing data, the MMRM model described in [Section 4.4.1.2](#) will be repeated using the LOCF approach for the mITT population (Table 14.2.2.2.3) and the PP population (Table 14.2.2.2.4).

4.4.2 Secondary Efficacy Endpoints

All secondary endpoint analyses will be performed on the mITT population. Other than the sequential testing strategy for comparing the change from baseline in the number of bleeding sites between products (see [Section 4.4](#)), there will be no adjustment for multiplicity performed for any other secondary endpoints detailed in this section.

4.4.2.1 Change from Baseline in Number of Bleeding Sites

The number of bleeding sites for each subject at each visit is calculated using the BI score, and descriptive statistics and frequency counts will be presented for the mITT population as detailed in [Section 4.4.1.1](#).

4.4.2.1.1 Statistical Hypothesis, Model and Method of Analysis

For comparisons to baseline within each treatment group, the following null and alternative hypotheses will be evaluated for post-baseline time points at Week 3 and Week 6 (for the Test Product group and the Reference Product group), and at Week 12 (for the Reference Product group) respectively:

- H_0 : There is no difference in the number of bleeding sites from baseline.
- H_1 : There is a treatment effect on the number of bleeding sites compared to baseline.

For comparisons to negative control, the following null and alternative hypotheses will be evaluated for post-baseline time points at Week 3, Week 6, and Week 12, respectively:

- H_0 : There is no difference in change from baseline in the number of bleeding sites in the Test Product group compared to the Reference Product group.
- H_1 : There is a difference in change from baseline in the number of bleeding sites in the Test Product group compared to the Reference Product group.

The results from the MMRM described in [Section 4.4.1.2](#) will be used to test the above hypotheses.

The LS mean change from baseline number of bleeding sites will be presented for each study product at each post-baseline time point with corresponding 95% CIs and p-values to test for a non-zero change from baseline.

The difference in LS mean change from baseline number of bleeding sites (Test Product – Reference Product) will also be presented at each post-baseline time point with corresponding 95% CIs and p-values to test for a non-zero difference ([Table 14.2.2.2.1](#)).

The assumption of normality and homogeneity of variance in the MMRM will be investigated. In case of violation of these assumptions, a Wilcoxon Rank Sum test (between products comparisons) and Wilcoxon Signed Rank Test (within product comparisons with baseline) will be performed to support the MMRM results.

The MMRM model will be repeated using the LOCF approach for the mITT population ([Table 14.2.2.2.3](#)) and the PP population ([Table 14.2.2.2.4](#)).

4.4.2.2 Change from Baseline in Bleeding Index (BI)

The BI will be assessed at each evaluable tooth site for each subject at each visit as described in [Section 4.4.1.1](#), according to the scoring system in [Table 4-1](#). The BI score for each subject at each visit is calculated as the sum of index values over all evaluable tooth sites, divided by the number of evaluable tooth sites. Evaluable tooth sites are those scored as 0, 1 or 2, so the BI score has a range of 0 to 2.

Descriptive statistics (n, mean, SD, SE, median, minimum, and maximum) will be presented for the BI score at each time point (absolute value, change from baseline and percent change

from baseline) in Table 14.2.3.1.1. Raw means (\pm SE) of the BI score at each time point will be plotted by study product in Figure 14.2.3.1.3 for all subjects in the mITT population.

Additionally, the number and percentage of subjects whose BI score has reduced (improved), remained the same and increased (worsened), respectively compared to baseline, will be presented by study product at each time point in Table 14.2.3.1.2 for the mITT population.

Individual data for the BI assessment at each evaluable tooth site will be listed for each subject in Listing 16.2.6.2.1, and individual data for the derived BI score will be listed for each subject in Listing 16.2.6.2.2, by study product group and visit for all randomized subjects.

4.4.2.2.1 Statistical Hypothesis, Model and Method of Analysis

For comparisons to baseline within each treatment group, the following null and alternative hypotheses will be evaluated for post-baseline time points at Week 3, Week 6 and Week 12, respectively:

- H_0 : There is no difference in the BI score from baseline.
- H_1 : There is a treatment effect on the BI score compared to baseline.

For comparisons to negative control, the following null and alternative hypotheses will be evaluated for post-baseline time points at Week 3, Week 6, and Week 12, respectively:

- H_0 : There is no difference in change from baseline in the BI score in the Test Product group compared to the Reference Product group.
- H_1 : There is a difference in change from baseline in the BI score in the Test Product group compared to the Reference Product group.

A MMRM will be used as described in [Section 4.4.1.2](#), with change from baseline in BI score as the dependent variable and baseline BI score as a covariate instead of baseline number of bleeding sites.

Using the above model, the LS mean change from baseline BI score will be presented for each study product at each post-baseline time point with corresponding 95% CIs and p-values to test for a non-zero change from baseline.

The difference in LS mean change from baseline BI score (Test Product – Reference Product) will also be presented at each post-baseline time point with corresponding 95% CIs and p-values to test for a non-zero difference (Table 14.2.3.2.1).

The assumption of normality and homogeneity of variance in the MMRM will be investigated. In case of violation of these assumptions, a Wilcoxon Rank Sum test (between products comparisons) and Wilcoxon Signed Rank Test (within product comparisons with baseline) will be performed to support the MMRM results.

The MMRM model will be repeated using the LOCF approach for the mITT population (Table 14.2.3.2.2).

4.4.2.3 Change from Baseline in Modified Gingival Index (MGI)

The MGI will be assessed on the facial and lingual surfaces of each scorable tooth (7-7 in each arch). Two scores (according to the scale in [Table 4-2](#) below) should be recorded buccally/labially (papilla and margin) and two scores lingually/palatally (papilla and margin). At each visit, each subject therefore has up to 112 evaluable tooth sites (i.e. 4 measurements on up to 28 scorable teeth).

Table 4-2 Modified Gingival Index Scoring System

Score Description	
0	Absence of inflammation
1	Mild inflammation; slight change in colour, little change in colour; little change in texture of any portion of the marginal or papillary gingival unit
2	Mild inflammation; criteria as above but involving the entire marginal or papillary gingival unit
3	Moderate inflammation; glazing, redness, edema, and/ or hypertrophy of the marginal or papillary gingival unit
4	Severe inflammation; marked redness, edema and/ or hypertrophy of the marginal or papillary gingival unit, spontaneous bleeding, congestion, or ulceration
9	Missing tooth or not qualified tooth

The MGI score for each subject at each visit is calculated as the sum of index values over all evaluable tooth sites, divided by the number of evaluable tooth sites. Evaluable tooth sites are those scored as 0, 1, 2, 3 or 4 so the MGI score has a range of 0 to 4.

Descriptive statistics (n, mean, SD, SE, median, minimum, and maximum) will be presented for the MGI score at each time point (absolute value, change from baseline and percent change from baseline) in [Table 14.2.4.1.1](#). Raw means (\pm SE) of the MGI score at each time point will be plotted by study product in [Figure 14.2.4.1.3](#) for all subjects in the mITT population.

Additionally, the number and percentage of subjects whose MGI score has reduced (improved), remained the same and increased (worsened), respectively compared to baseline, will be presented by study product at each time point in [Table 14.2.4.1.2](#) for the mITT population.

Individual data for the MGI assessment at each evaluable tooth site will be listed for each subject in [Listing 16.2.6.3.1](#), and individual data for the derived MGI score will be listed for each subject in [Listing 16.2.6.3.2](#), by study product group and visit for all randomized subjects.

4.4.2.3.1 Statistical Hypothesis, Model and Method of Analysis

For comparisons to baseline within each treatment group, the following null and alternative hypotheses will be evaluated for post-baseline time points at Week 3, Week 6, and Week 12, respectively:

- H_0 : There is no difference in the MGI score from baseline.
- H_1 : There is a treatment effect on the MGI score compared to baseline.

For comparisons to negative control, the following null and alternative hypotheses will be evaluated for post-baseline time points at Week 3, Week 6, and Week 12, respectively:

- H_0 : There is no difference in change from baseline in the MGI score in the Test Product group compared to the Reference Product group.
- H_1 : There is a difference in change from baseline in the MGI score in the Test Product group compared to the Reference Product group.

A MMRM will be used as described in [Section 4.4.1.2](#), with change from baseline in MGI score as the dependent variable and baseline MGI score as a covariate instead of baseline number of bleeding sites.

Using the above model, the LS mean change from baseline MGI score will be presented for each study product at each post-baseline time point with corresponding 95% CIs and p-values to test for a non-zero change from baseline.

The difference in LS mean change from baseline MGI score (Test Product – Reference Product) will also be presented at each post-baseline time point with corresponding 95% CIs and p-values to test for a non-zero difference (Table 14.2.4.2.1).

The assumption of normality and homogeneity of variance in the MMRM will be investigated. In case of violation of these assumptions, a Wilcoxon Rank Sum test (between products comparisons) and Wilcoxon Signed Rank Test (within product comparisons with baseline) will be performed to support the MMRM results.

The MMRM model will be repeated using the LOCF approach for the mITT population (Table 14.2.4.2.2).

4.4.2.4 Change from Baseline in Turesky Plaque Index (TPI)

The TPI will be used to assess plaque on all gradable teeth meeting the inclusion/exclusion criteria (natural teeth only). The TPI will be assessed on the facial and lingual surfaces of each scorable tooth (7-7 in each arch). Three scores (according to the scale in [Table 4-3](#) below) should be recorded buccally/labially (distal, body and mesial sites) and three scores lingually/palatally (distal, body and mesial sites). At each visit, each subject therefore has up to 168 evaluable tooth sites (i.e. 6 measurements on up to 28 scorable teeth).

Table 4-3 Turesky Plaque Index Scoring System

Score Description	
0	No plaque
1	Separate flecks of plaque at the cervical margin
2	Thin continuous band of plaque (up to 1 mm) at the cervical margin
3	Band of plaque wider than 1 mm but covering < 1/3 of the tooth surface
4	Plaque covering ≥ 1/3 but < 2/3 of the tooth surface
5	Plaque covering ≥ 2/3 of the tooth surface

Score Description

9 Missing tooth or not qualified tooth

The overall TPI score for each subject at each visit is calculated as the sum of index values over all evaluable tooth sites, divided by the number of evaluable tooth sites. Evaluable tooth sites are those scored as 0, 1, 2, 3, 4 or 5 so the overall TPI score has a range of 0 to 5.

The interproximal TPI score for each subject at each visit is calculated as the sum of index values over all evaluable distal and mesial tooth sites, divided by the number of evaluable distal and mesial tooth sites. Similar to the overall TPI score, the interproximal TPI score has a range of 0 to 5.

Descriptive statistics (n, mean, SD, SE, median, minimum, and maximum) will be presented at each time point (absolute value, change from baseline and percent change from baseline) in Table 14.2.5.1.1 for overall TPI score and in Table 14.2.5.1.3 for interproximal TPI score. Raw means (\pm SE) at each time point will be plotted by study product in Figure 14.2.5.1.5 for overall TPI score and in Figure 14.2.5.1.6 for interproximal TPI score, for the mITT population.

Additionally, the number and percentage of subjects whose score has reduced (improved), remained the same and increased (worsened), respectively compared to baseline, will be presented by study product at each time point in Table 14.2.5.1.2 (overall TPI score) and Table 14.2.5.1.4 (interproximal TPI score) for the mITT population.

Individual data for the TPI assessment at each evaluable tooth site will be listed for each subject in Listing 16.2.6.4.1, and individual data for the derived TPI score (overall and interproximal, respectively), will be listed for each subject in Listing 16.2.6.4.2, by study product group and visit for all randomized subjects.

4.4.2.4.1 Statistical Hypothesis, Model and Method of Analysis

For comparisons to baseline within each treatment group, the following null and alternative hypotheses will be evaluated for post-baseline time points at Week 3, Week 6, and Week 12, for the overall TPI score and interproximal TPI score, respectively:

- H_0 : There is no difference in the TPI score from baseline.
- H_1 : There is a treatment effect on the TPI score compared to baseline.

For comparisons to negative control, the following null and alternative hypotheses will be evaluated for post-baseline time points at Week 3, Week 6 and Week 12, for the overall TPI score and interproximal TPI score, respectively:

- H_0 : There is no difference in change from baseline the TPI score in the Test Product group compared to the Reference Product group.
- H_1 : There is a difference in change from baseline in the TPI score in the Test Product group

Separate MMRMs will be used as described in [Section 4.4.1.2](#), with change from baseline in TPI score (overall and interproximal, respectively) as the dependent variable and baseline TPI score (overall and interproximal, respectively) as a covariate instead of baseline number of bleeding sites.

Using the above model, the LS mean change from baseline TPI score will be presented for each study product at each post-baseline time point with corresponding 95% CIs and p-values to test for a non-zero change from baseline.

The difference in LS mean change from baseline TPI score (Test Product – Reference Product) will also be presented at each post-baseline time point with corresponding 95% CIs and p-values to test for a non-zero difference (Table 14.2.5.2.1 for overall TPI, and Table 14.2.5.2.3 for interproximal TPI).

The assumption of normality and homogeneity of variance in the MMRM will be investigated. In case of violation of these assumptions, a Wilcoxon Rank Sum test (between products comparisons) and Wilcoxon Signed Rank Test (within product comparisons with baseline) will be performed to support the MMRM results.

The MMRM model will be repeated using the LOCF approach for the mITT population (Table 14.2.5.2.2 for overall TPI, and Table 14.2.5.2.4 for interproximal TPI).

4.4.3 Handling of Missing Values/Censoring/Discontinuations

For the primary analyses, missing data will not be replaced or imputed. Subjects who withdraw from the study prematurely will be included in the statistical analyses up to the point of discontinuation. Subjects who withdraw will not be replaced. In the event that a subject has no individual BI, MGI or TPI assessments available at a given visit, the number of bleeding sites, BI score, MGI score or TPI score will also be considered as missing for that visit.

Experience in previous, similar studies suggest missing data will not be prevalent. The SAS Proc Mixed implementation of the repeated measures analysis of covariance (ANCOVA) that will be used in almost all analyses, implicitly imputes any missing data based on the non-missing observations. The basic theory on which Proc Mixed is based holds even with missing data as long as the missing data are missing at random.

An additional analysis will explore the sensitivity of results to the effect of missing data on the primary and secondary efficacy endpoints. The sensitivity analysis will use the same MMRM model, but with LOCF for missing data. Only post-baseline results may be carried forward.

4.5 Analysis of Safety

The safety profile of the study products will be assessed with respect to adverse events (AEs), incidents and OST/OHT abnormalities in this oral health study.

4.5.1 Adverse Events and Serious Adverse Events

All AEs will be reviewed by the Clinical Research Scientist or Designee prior to database lock and unblinding, and will be coded to a system organ class (SOC) and preferred term (PT) using the Medical Dictionary for Regulatory Activities (MedDRA).

AEs will be classified as oral and non-oral on the AE page of eCRF.

Treatment emergent adverse events (TEAEs) are defined as new AEs that occur on or after the first study product use (if this date is missing, a suitable alternative will be used e.g. date of randomization). AEs with an onset date/time prior to the first study product use will be considered as non-treatment emergent.

The following summary tables and listings will be presented by study product group.

- Table of TEAEs by SOC and PT (Table 14.3.1.1)
- Table of TEAEs by Oral/Non-Oral and PT (Table 14.3.1.2)
- Table of treatment related TEAEs by SOC and PT (Table 14.3.1.3)
- Table of treatment related TEAEs by Oral/Non-Oral and PT (Table 14.3.1.4)
- Table of AEs related to COVID-19 by SOC and PT (Table 14.3.1.5)
- Table of non-serious TEAEs by SOC and PT (Table 14.3.1.6) [only produced if there are more than 5 AEs]
- Table of serious TEAEs by SOC and PT (Table 14.3.1.7) [only produced if there are more than 5 serious TEAEs]
- Listing of all AEs (Listing 16.2.7.1 for all randomized subjects; Listing 16.2.7.2 for non-randomized subjects)
- Listing of deaths (Listing 14.3.2.1)
- Listing of non-fatal SAEs (Listing 14.3.2.2)
- Listing of TEAEs leading to study or product withdrawal (Listing 14.3.2.3)
- Listing of TEAEs classified as Oral (Listing 14.3.2.4)
- Listing of all AEs related to COVID-19 (Listing 16.2.7.3 for all screened subjects)

All incidents will be listed in Listing 16.2.7.4.

In the event that there is nothing to report, a null table or listing will be produced.

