#### 9.3.1 Oral Soft Tissue Examination (OST)

Where possible, this procedure should be conducted by a single dental examiner or clinically qualified designee. The OST examination will be accomplished throughout the study by direct observation and palpation with retraction aids as appropriate. The examiner will include examination of the labial mucosa (including lips), buccal mucosa, mucogingival folds, gingival mucosa, hard palate, soft palate, tonsillar area, pharyngeal area, tongue, sublingual area, submandibular area and salivary glands.

The results of the examination will be recorded in the CRF as either normal or abnormal, with details of any abnormalities. Any post-treatment soft tissue abnormality, or worsening of a pre-existing condition, observed by the examiner or reported by the subject will be recorded on the CRF. Any abnormalities or worsening of a pre-existing condition observed by the clinical examiner or reported by the subject from the OST examination carried out at Screening will be recorded as an AE.

During the oral examination, if any abnormalities on the oral soft tissues are detected, the subject will be advised to seek further medical/ dental advice from their dentist or general medical practitioner as deemed appropriate in the opinion of the clinical examiner.

Findings from this examination at Screening will be used to determine subject eligibility.

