#### Events Meeting the AE Definition:

- Any abnormal laboratory test results (hematology, clinical chemistry, or urinalysis) or other safety assessments (e.g. ECG, radiological scans, vital sign measurements), including those that worsen from baseline, considered clinically significant in the medical and scientific judgment of the investigator (i.e., not related to progression of underlying disease).
- Exacerbation of a chronic or intermittent pre-existing condition including either an increase in frequency and/or intensity of the condition.
- New conditions detected or diagnosed after study product administration even though it may have been present before the start of the study.
- Signs, symptoms, or the clinical sequelae of a suspected drug-drug interaction.
- Signs, symptoms, or the clinical sequelae of a suspected overdose of either study product or a concomitant medication. Overdose per se will not be reported as an AE/SAE unless it is an intentional overdose taken with possible suicidal/self-harming intent. Such overdoses should be reported regardless of sequelae.
- "Lack of efficacy" or "failure of expected pharmacological action" per se will not be reported as an AE. Such instances will be captured in the efficacy assessments. However, the signs, symptoms, and/or clinical sequelae resulting from lack of efficacy will be reported as AE if they fulfill the definition of an AE.

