### **10.3 Time Period and Frequency for Collecting AE and SAE Information**

All AEs, and therefore all SAEs will be collected immediately after a subject provides consent to participate in the study by the completion (signature) of the ICF and until 5 days following last administration of the study product (or last procedure).

Medical occurrences that began before obtaining informed consent will be recorded in the Medical History/Current Medical Conditions section of the CRF not the AE section.

Details recorded by the subject on a diary or similar document that meet the definition of an AE must also be discussed with the subjects and transcribed in the AE section of the CRF.

All SAEs will be recorded and reported to the sponsor or designee immediately and under no circumstance should this exceed 24 hours. The investigator will submit any updated SAE data to the sponsor within 24 hours of it being available.

Investigators are not obligated to actively seek AEs or SAEs after the conclusion of the study participation. However, if the investigator learns of any SAE, including a death, at any time after a subject has been discharged from the study, and he/she considers the event to be reasonably related to the study product or study participation, the investigator must promptly notify the sponsor.

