## 10.6 Follow-up of AEs and SAEs

After the initial AE/SAE report, the investigator is required to proactively follow up with each subject and provide further information on the subject’s condition.

All AEs (serious and non-serious) will be followed until resolution, until the condition stabilizes, until the event is otherwise explained, or until the subject is lost to follow-up.

The investigator is obligated to perform or arrange for the conduct of supplemental measurements and/or evaluations as may be indicated or as requested by the sponsor to elucidate as fully as possible the nature and/or causality of the AE. This may include additional laboratory tests or investigations, histopathological examinations, or consultation with other health care professionals.

New or updated information will be recorded on the AE CRF page and on the SAE form (subject to the classification of the AE).

The investigator will submit any updated SAE data to the sponsor within 24 hours of receipt of the information.

Investigators are not obliged to actively seek AEs in former subjects. However, if the investigator learns of a SAE, including death, at any time after a subject has been discharged from the study, and considers the event reasonably related to the study product or study participation, the investigator will promptly notify the sponsor by emailing the information to the Case Management Group mailbox at the sponsor **PPD** with copy to the appropriate sponsor Study Manager.

The investigator will submit any updated SAE data to the sponsor within the designated reporting time frames.

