### 12.3.3 Safety Analysis(es)

The Safety population will be used for safety analyses. Safety analyses will be performed according to product received. All AEs will be reviewed by the Clinical Research Scientist, or designee, prior to database lock and unblinding and will be coded using the MedDRA. During this review stage, AEs will be further categorized as oral or non-oral. AEs will be listed and summarized by product received. SAEs will also be listed. AEs will be regarded as 'treatment' emergent if they occur on or after the first product use at the Baseline visit.

The following AEs tables will be produced, presented by product group:

- listing of all AEs (randomized subjects and non-randomized subjects);
- summary of AEs;
- treatment emergent AEs by Oral/Non-Oral and Preferred Term (PT);
- treatment emergent AEs by System Organ Class (SOC) and PT;
- treatment related AEs by Oral/Non-Oral and PT;
- listing of serious AEs (if there are no SAEs, a null listing will be produced; if there are more than 5 treatment emergent serious AEs (SAEs), a table will be produced in place of the listing by SOC and PT);
- non-serious treatment emergent AEs by SOC and PT (only produced if there are more than 5 AEs).

The results of the OST and OHT examinations will be listed and the results of the OST examinations will be tabulated.

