1.2 Study Objectives

Study objectives and endpoints are defined in [Table 1-2](#).

Table 1-2 Study Objectives and Endpoints

Objectives	Endpoints
Primary Objective	Primary Endpoint
To evaluate the efficacy of a dentifrice containing 67% w/w sodium bicarbonate and 0.310% w/w sodium fluoride, compared to its baseline, for the assessment of gingivitis, as measured by the number of bleeding sites after 12 weeks twice daily toothbrushing.	Number of bleeding sites at 12 weeks, compared to baseline
Secondary Objectives	Secondary Endpoints
Efficacy	
To evaluate the efficacy of a dentifrice containing 67% w/w sodium bicarbonate and 0.310% w/w sodium fluoride, compared to negative control, for the assessment of gingivitis, as measured by the number of bleeding sites after 12 weeks twice daily toothbrushing.	Number of bleeding sites at 12 weeks, compared to negative control
To evaluate the efficacy of a dentifrice containing 67% w/w sodium bicarbonate and 0.310% w/w sodium fluoride for the assessment of gingivitis, as measured by the number of bleeding sites after 3 and 6 weeks twice daily toothbrushing.	Number of bleeding sites at 3 and 6 weeks, compared to baseline and negative control
To evaluate the efficacy of a dentifrice containing 67% w/w sodium bicarbonate and 0.310% w/w sodium fluoride for the assessment of gingivitis, as measured by the Bleeding Index (BI) after 3, 6 and 12 weeks twice daily toothbrushing.	Mean BI at 3, 6 and 12 weeks, compared to baseline and negative control
To evaluate the efficacy of a dentifrice containing 67% w/w sodium bicarbonate and 0.310% w/w sodium fluoride for the assessment of gingivitis, as measured by the Modified Gingival Index (MGI) after 3, 6 and 12 weeks twice daily toothbrushing.	Mean MGI at 3, 6 and 12 weeks, compared to baseline and negative control
To evaluate the efficacy of a dentifrice containing 67% w/w sodium bicarbonate and 0.310% w/w sodium fluoride for the assessment of plaque accumulation, as measured by the Turesky Plaque Index (TPI, overall and interproximal) after 3, 6, and 12 weeks twice daily brushing.	Mean TPI (overall and interproximal) at 3, 6 and 12 weeks, compared to baseline and negative control
Safety	
To assess the oral tolerability of a dentifrice containing 67% w/w sodium bicarbonate and 0.310% w/w sodium fluoride, over 12 weeks twice daily use.	Treatment-emergent adverse events over 12 weeks

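### The treatment-emergent AE definition has no worsening clause, so an AE open from washout that worsens on study product may or may not be counted, depending on how the site records it

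*SAP*

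**What the plan says.** SAP 1.2 names one safety endpoint, "Treatment-emergent adverse events over 12 weeks", in support of the oral tolerability objective.

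SAP 4.5.1 defines it in two steps: "Treatment emergent adverse events (TEAEs) are defined as new AEs that occur on or after the first study product use", followed by "AEs with an onset date/time prior to the first study product use will be considered as non-treatment emergent". Protocol 12.3.3 is shorter. It regards AEs as treatment "emergent if they occur on or after the first product use at the Baseline visit". It contains neither the word *new* nor the explicit exclusion of earlier onsets, and it is also silent on worsening. SAP Table 5-1, which lists departures from the protocol analysis, does not mention this difference.

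Three recording rules in the protocol bear on the question:

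- Section 10.1 lists as an AE "Exacerbation of a chronic or intermittent pre-existing condition including either an increase in frequency and/or intensity of the condition".
- Section 10.6, on follow-up of AEs already reported, says: "New or updated information will be recorded on the AE CRF page and on the SAE form".
- Section 10.3 says: "Medical occurrences that began before obtaining informed consent will be recorded in the Medical History/Current Medical Conditions section of the CRF not the AE section".

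Protocol 9.3.1 and 9.3.2, repeated in SAP 4.5.2.1 and 4.5.2.2, add that abnormalities, or worsening of an existing condition, "from the OST examination carried out at Screening will be recorded as an AE" (9.3.2 has the same sentence for the OHT examination).

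**The concern.** AE collection opens at consent, and the AE definition in Protocol 10.1 extends to the washout product. Some subjects can therefore reach first use of study product with an AE already open. For a dentifrice, aggravation of a mild existing mouth complaint is one of the forms an oral tolerability problem could take. A TEAE definition that looks only at onset date, with no worsening clause, does not reliably capture it.

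The omission need not fall evenly on the two arms. The washout dentifrice and the reference dentifrice are the same marketed product (Protocol Tables 6-1 and 6-2), so only the test arm changes toothpaste at Baseline. Aggravation caused by the change of product would arise in the test arm, which is the arm the tolerability objective concerns.

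**Working it through.** No figure in the plan is at issue, so the check is textual.

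**1. Can an AE start before first use?** Yes. Collection starts at consent (Protocol 10.3), and Baseline follows Screening by 14±3 days, that is 14 − 3 = 11 to 14 + 3 = 17 days. The OST and OHT examinations at Visit 2 come before the supervised brushing in the order of procedures (Protocol 8.2.1), so a finding first seen there also precedes first use.

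**2. What does the SAP do with it?** SAP 4.5.1 classes it as non-treatment emergent by its onset date, with no exception.

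**3. What happens if it then worsens on study product?** The result depends on data entry:

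| Site action | Onset date on record | Class under SAP 4.5.1 | Where it appears |
|---|---|---|---|
| Updates the open AE record | Washout | Non-treatment emergent | Listing 16.2.7.1; also 14.3.2.1 or 14.3.2.2 if fatal or serious |
| Enters the exacerbation as a new AE | After first use | Treatment emergent | TEAE tables and listings |

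On the first route the event is absent from Tables 14.3.1.1 to 14.3.1.4, 14.3.1.6 and 14.3.1.7. It is also absent from Listing 14.3.2.3 (TEAEs leading to withdrawal) and Listing 14.3.2.4 (oral TEAEs), even if the worsening was the reason for withdrawal.

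**4. Do the documents choose between the routes?** No.

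- Protocol 10.1 makes an exacerbation an AE but does not say that it needs its own record when the condition is already on the AE page.
- Protocol 10.6 sends updates to the AE page. It does not say whether that means the same record, and it does not mention onset date.
- Protocol 10.5.1 assigns each AE to one intensity category and does not say what to do when the intensity changes.
- SAP 4.5.1 has no derivation for a change in intensity.

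**5. Would another display show the worsening?** Not as a count. Table 14.3.4.1 classifies OST by visit as abnormal, not abnormal or not examined, so a lesion present at Baseline and worse later is abnormal at both visits. OHT findings are only listed.

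**The case against.** The strongest reply is that Protocol 10.1 already treats an exacerbation as an AE. Entered with the date of worsening, it meets both TEAE definitions. This stands. A reader might infer from SAP 4.5.1 alone that every washout AE that worsens is left out of the endpoint. The documents do not support that: exclusion follows only if the existing record is updated, and Protocol 10.6 neither requires that nor fixes the onset date. CRF completion instructions are not among the documents and may settle the matter.

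A reader might also infer that the Screening sentence in Protocol 9.3.1 and 9.3.2 contradicts 10.3, by making findings that predate consent into AEs when 10.3 sends them to Medical History. That is one reading of an ambiguous sentence. Screening is the first examination, the sentence refers to worsening, and in 9.3.1 the sentence before it concerns findings after treatment. It can equally mean changes since Screening, and then there is no conflict. Because this text addresses worsening directly, the case is weaker for oral findings already present at Screening. It is stronger for an AE already open from washout.

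Finally, the data are not lost: every AE in a randomized subject is in Listing 16.2.7.1, and the death and non-fatal SAE listings are not restricted to TEAEs. That is true, but a listing is not the endpoint count.

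**Conclusion.** The point holds in a limited form. SAP 4.5.1 excludes every pre-use onset, neither document has a worsening clause, and no section requires a new record when an open washout AE worsens. Such an event *can* be left out of the TEAE tables and of Listings 14.3.2.3 and 14.3.2.4. Two clinically identical events could be classified differently because of data-entry habit alone, and the single safety endpoint should not depend on that.

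The size is unknown. The documents give no AE rates, no rate of worsening, and no indication of how often sites would update a record rather than open a new one. The conclusion assumes that no CRF instruction outside these documents already requires a new record. If one does, only the SAP wording needs to catch up. The possible imbalance between arms follows from the design and is not a demonstrated effect.

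**What to change.** 1. In SAP 4.5.1, define a TEAE as an AE that begins at or after first use of study product, or one present before first use that increases in intensity, frequency or seriousness from that point on.
2. State in the SAP and in the CRF completion guidelines that such worsening is entered as a new AE record with its own onset date.
3. Align Protocol 12.3.3 with this definition, or list the change in SAP Table 5-1.
4. Clarify whether the Screening sentence in Protocol 9.3.1 and 9.3.2 and in SAP 4.5.2.1 and 4.5.2.2 means changes since Screening, so that it is consistent with Protocol 10.3.

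The cost is minor wording in the SAP, the protocol and the CRF guidelines, to be settled before unblinding. Slightly more TEAEs may be reported.
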